An intent-to-treat analytic approach will be employed. Multiple imputation will be utilized for subjects who discontinue during the study and do not complete the post-treatment assessment. Multiple imputation is desirable because instead of filling in a single value for each missing data point, each missing value is replaced with a set of plausible values, creating multiple imputed datasets. These datasets are then analyzed using standard procedures (that would be appropriate for a single, complete dataset), and results from the multiple data sets are combined into one set of results. The SAS procedures MI and MIANALYZE will be used for creating and analyzing multiple imputed data, resulting in statistically valid results that appropriately reflect the uncertainty due to missing values.

Multiple imputation is a useful method for analysis of datasets with data that are plausibly missing at random (MAR). Missing values rarely occur completely at random (MCAR). Instead, missing values are typically based on other variables, so they are MAR. During the multiple imputation process, the analyst should use all observed variables available in predicting missing values (even variables not used in analysis). If these variables are useful for predicting missing values, the multiple imputation increases power. Furthermore, by using an exhaustive set of predictor variables, the multiple imputation process creates a largely MAR dataset. Thus, multiple imputation can convert missing not at random (MNAR) data to MAR.

Simulation was used to determine sample size needed for analyzing multiple imputed datasets. We assume N=90 completers in each group, so a simulated dataset with N=180 subjects was created. Change in PAPA MDD severity sum scores were generated assuming normally distributed scores with a SD of 4.69 (pooled SD from our pilot RCT) and a mean difference in change scores in the two groups of 2.5. The demographic variables gender, age, race, family income, parental education level, and parental marital status were also included in this dataset. To simulate demographic characteristics, complete demographic profiles from the subjects in our pilot RCT were drawn with replacement 180 times and randomly assigned to the 180 simulated cases. A general linear model of change in PAPA MDD severity sum score by group was conducted for this simulated dataset.

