To address differential dropout and its impact on power, we assume a 25% drop-out rate in the PCIT-ED group and a 30% drop-out rate in the WL group. So 25% and 30% of the simulated PCIT-ED and WL subjects' MDD severity sum change scores were set to missing, respectively, using a random number generator. Because the simulated missingness was random, missing values are not predicted by anything, so data are missing completely at random (MCAR). This should be realistic for the multiple imputation power analysis that follows.

The SAS v9.2 MI procedure was used to create multiple imputed datasets with MDD severity sum change scores based on the simulated demographic variables in the dataset. Multiple imputation was conducted 10 times, with 10 imputed datasets created. The SAS v9.2 MIANALYZE procedure was then used to run a general linear model of change scores by group for each set of multiple imputed datasets. Table 5 shows the results of the general linear model in the complete simulated dataset and then each of the 10 multiple imputed datasets.

Dataset	Estimate	SE	SE ²	t	p
Complete Simulated Dataset	-2.278	0.729	0.532	-3.12	0.0021
Multiple Imputed Dataset 1	-2.307	0.745	0.555	-3.10	0.0020
Multiple Imputed Dataset 2	-1.951	0.855	0.731	-2.28	0.0241
Multiple Imputed Dataset 3	-2.090	0.569	0.756	-2.40	0.0182
Multiple Imputed Dataset 4	-2.121	0.848	0.718	-2.50	0.0137
Multiple Imputed Dataset 5	-2.063	0.816	0.666	-2.53	0.0122
Multiple Imputed Dataset 6	-1.894	0.796	0.633	-2.38	0.0178
Multiple Imputed Dataset 7	-2.220	0.824	0.679	-2.69	0.0078
Multiple Imputed Dataset 8	-2.079	0.846	0.715	-2.46	0.0152
Multiple Imputed Dataset 9	-2.121	0.850	0.723	-2.49	0.0141
Multiple Imputed Dataset 10	-2.124	0.845	0.714	-2.51	0.0128
Mean	-2.097		0.689		
Variance	0.014				

Rubin's method for determining the uncertainty of the imputed estimate was employed. Following this method, the total variance from the imputed datasets is $T = (\text{mean within-imputation variance}) + (1 + 1/(N \text{ sets of imputed datasets})) * (\text{between-imputations variance})$

= $0.689 + 1.1 * 0.014 = 0.704$. The SE^2 of the model conducted on the complete simulated dataset is 0.532. The ratio of these two values is $0.704/0.532 = 0.32$.

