So, the relative increase in variance due to missing values is 32%, indicating that $1.32 * 180$ subjects = 238 subjects are required to attain the same power that would be attained in a sample of 180 subjects who all complete the study. In other words, 238 subjects must be enrolled in the study, with 180 completing, to achieve the same power when using multiple imputation as would be achieved if 180 subjects were enrolled and all completed. If multiple imputation were not used, and only complete cases were analyzed, approximately 238 subjects would have to be enrolled to produce 180 complete cases. Thus, multiple imputation is more efficient than complete-case analysis, in addition to avoiding bias due to MAR missingness.

A secondary analytic approach will be to use mixed models on non-imputed data. Mixed models can be used to analyze repeated measures data without discarding subjects with missing data. Mixed models will be used for measures only obtained at pre- and post-assessment and on measures with interval assessments. Analytic approaches for each set of specific aims and hypotheses are detailed below.

Specific Aim 1: To conduct an RCT of an early dyadic intervention for PO-MDD, PCIT-ED, compared to a WL control condition.

Hypothesis 1A: Compared to those randomized to the WL, preschoolers who are first randomized to PCIT-ED will show significantly increased rates of remission, greater reductions in MDD symptoms, and decreases in impairment.

Hypothesis 1B: Compared to those randomized to the WL, preschoolers who are first randomized to PCIT-ED will show significantly greater increases in emotional competence measured by the ability to accurately identify emotions in themselves and others and the ability to effectively regulate intense emotions.

Hypothesis 1C: Compared to those on the WL, parents who are first randomized to PCIT-ED will show significantly greater increases in emotion skill learning (ESL) and reductions in MDD symptoms and parenting stress.

Analytic Approach: Continuous post-assessment scores will be compared between PCIT-ED and WL groups using analysis of covariance, covarying for pre-assessment scores. The stratification variables, gender and externalizing comorbid diagnoses, will also be included as covariates in the models.

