PFC-Scale and PAPA MDD severity sum scores will be used to assess differences in depressive symptoms; HBQ and PAPA impairment scores will be analyzed to determine differences in functional impairment. Differences in emotion regulation (as an executive function) in the two groups will be examined using scores from the BRIEF-P; emotion development will be analyzed using scores from the ERC, Emotion Understanding, FACE, KIDSEDF, and the "Waiting" and "Puzzle" tasks. Post-assessment EDCl, BDI-II, and PSI scores will be compared between PCIT-ED and WL groups to determine differences in increases in Emotion Skill Learning and reduction of parental depressive symptoms and parenting stress.

Rates of remission (defined by 50% reduction in MDD severity and not meeting diagnostic criteria) will be compared in the PCIT-ED and WL subjects using logistic regression.

Interval assessment scores will also be analyzed across PCIT-ED and WL groups in repeated measures mixed models. In these models, repeated measures of PFC-Scale, HBQ MDD and externalizing co-morbidity severity and impairment, PSI and ESL (measured by EDCl) at pre-assessment, 6-week assessment, 12-week assessment, and post-assessment will be compared between the PCIT-ED and WL groups.

In addition to the analyses described above, pre-assessment variables that could possibly be associated with outcome, such as subject age and maternal depression, will be investigated as potential predictors of outcome.

Specific Aim 2: To investigate mediators and moderators of treatment effects.

Hypothesis 2A: Parental emotion skill learning (ESL) will mediate treatment effects. Child depression outcomes will be mediated by parental ESL.

Hypothesis 2B: Parental Emotional Intelligence (EI, a stable trait measured at baseline by MSCEIT) will be a moderator of ESL and child outcome. Parents with higher EI will show better ESL, and as a result, children of parents with high EI will show better outcomes than children of parents with low EI.

Analytic Approach: Parental ESL will be measured with the Emotion Development Coding instrument. This is an itemized assessment of parents' emotion skill learning. Each item is rated as 3=satisfactory, 2=needs practice, or 1=not evident. The total ESL score will be calculated as the mean of these items.

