To assess parental ESL as a potential mediator of the relationship between treatment group and child treatment response, a macro (for SAS or SPSS) developed by Hayes will be utilized. For mediation analyses, the PROCESS macro estimates path coefficients in a mediation model and generates bootstrap confidence intervals for the indirect effects of the independent variable on the dependent variable through a mediator variable. It is also possible to include covariates not proposed to be mediators in the model. Paternal ESL will be evaluated by entering post ESL score into the model as a potential mediator, with treatment group as the independent variable and change in PAPA MDD severity sum score as the dependent variable.

Power for Mediation: To estimate power for this mediation analysis, the following steps were taken. First, we expect the difference in MDD severity sum change score in the two groups to be approximately 2.5, with a SD of 4.69 (based on our pilot study). With 90 subjects per group, an alpha of 0.05, and a 1-sided test, power=0.97. Next, we expect the correlation of change in MDD severity sum score and ESL score to be approximately 0.25. Using Fisher's Z transformation with a sample size of 180, the correlation of 0.25 transforms to $Z = \tanh(0.25) * \sqrt{180-3} = 3.398$. Subtracting 1.96 gives 1.438, corresponding to power=0.92. Thus, we will be well-powered to detect a mediation effect.

To assess parental emotional intelligence (EI) as a potential moderator of treatment response, the PROCESS macro will be used. For moderation analyses, the PROCESS macro

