Hypothesis 3: MDD remission (not meeting diagnostic criteria for ≥ 2 weeks) will be sustained at the 18 week follow-up in 80% of subjects who were in remission at the post-treatment assessment.

Analytic Approach: Rate of 18 week remission in subjects who met remission requirements at the post assessment will be calculated and compared to the 80% expected rate using a Chi-square goodness-of-fit test.

General Data Analysis Considerations: All outcome measures other than MDD diagnosis are continuous. The PFC-Scale and MDD severity scores from our pilot PCIT-ED and DEPI subjects were approximately normally distributed, as determined by the Shapiro-Wilk test. However, if these scores or other outcome scores are found to be from non-normal distributions, the data will be log- or power-transformed prior to analysis. Bonferroni correction will be used to limit the possibility of Type I errors for the main outcomes. A less conservative correction, such as the Bonferroni-Holm correction, will be applied for tests of other outcomes.

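### The main outcomes get single-step Bonferroni although Holm, named only for the other outcomes, guarantees the same family-wise error rate and is never less powerful

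*Combined protocol and SAP*

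**What the plan says.** The SAP's multiplicity rule is two sentences at the end of General Data Analysis Considerations. The first reads "Bonferroni correction will be used to limit the possibility of Type I errors for the main outcomes". The second reads "A less conservative correction, such as the Bonferroni-Holm correction, will be applied for tests of other outcomes". No reason is given for the split, and Holm is only an example in the second sentence, so the procedure for the other outcomes is not fixed either.

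The SAP speaks of main outcomes in the plural but does not list or count them. The nearest candidates are under Specific Aim 1. Hypothesis 1A predicts that children randomized to PCIT-ED first "will show significantly increased rates of remission, greater reductions in MDD symptoms, and decreases in impairment". The analytic approach then gives two measures for symptoms ("PFC-Scale and PAPA MDD severity sum scores will be used to assess differences in depressive symptoms"), two for impairment (HBQ and PAPA), and a logistic regression for remission.

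The only stated effect size and test-level power are under Power for Mediation: "we expect the difference in MDD severity sum change score in the two groups to be approximately 2.5, with a SD of 4.69", and then "With 90 subjects per group, an alpha of 0.05, and a 1-sided test, power=0.97". That power figure carries no multiplicity adjustment.

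**The concern.** The rule treats Holm as the laxer method and so keeps it away from the tests that matter most. Holm is less conservative, but the family-wise error rate it guarantees is no weaker. Both procedures hold that rate at or below alpha whatever the correlation between outcomes and whichever null hypotheses are true. They differ in power, and Holm is never worse. As written, the most important tests get the less powerful of two procedures with the same guarantee.

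At stake is power on individual main outcomes. Hypothesis 1A predicts benefit in three domains, and with a Bonferroni divisor on every test the trial is more likely to miss a real effect in one of them after showing an effect in another.

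**Working it through.** **Inputs**
- Difference in change scores 2.5, SD 4.69 (SAP, Power for Mediation and the sample-size simulation).
- 90 completers per group: "We assume N=90 completers in each group, so a simulated dataset with N=180 subjects was created".
- Alpha 0.05, one-sided, for the plan's own power figure.
- Assumptions, because the documents do not give them: number of main outcomes m = 2, 3 or 5; two-sided family-wise alpha 0.05; correlation 0.5 between test statistics; the effect on any outcome other than PAPA severity.

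**Step 1. Reproduce the plan's figure.** The expected test statistic is 2.5 / (4.69 × √(2/90)) = 3.576. One-sided at 0.05, power = Φ(3.576 − 1.645) = 0.973, which matches the stated 0.97. Two-sided at 0.05 without adjustment it is Φ(3.576 − 1.960) = 0.947.

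**Step 2. Bonferroni.** Each test uses 0.05/m, two-sided:
- m = 2: Φ(3.576 − 2.241) = 0.909
- m = 3: Φ(3.576 − 2.394) = 0.881
- m = 5: Φ(3.576 − 2.576) = 0.841

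**Step 3. Why Holm has the same guarantee.** Order the p-values. Compare the smallest with α/m, the next with α/(m − 1), and so on to α, stopping at the first failure. Suppose m₀ nulls are true. The first true null to be rejected is reached no later than step m − m₀ + 1, so its p-value is at most α/m₀. The chance that any of the m₀ true nulls has so small a p-value is at most m₀ × α/m₀ = α, with no assumption about dependence. Every Holm threshold is at least α/m, so every Bonferroni rejection is also a Holm rejection. The first step is the Bonferroni test itself, so the chance of at least one rejection is identical.

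**Step 4. Size of the loss, equal effects.** Simulation with 400,000 replicates per scenario, correlation 0.5, effect 2.5/4.69 = 0.533 on every outcome:

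| m | Per-outcome power, Bonferroni | Per-outcome power, Holm | At least one, both methods |
|---|---|---|---|
| 2 | 0.91 | 0.94 | 0.97 |
| 3 | 0.88 | 0.93 | 0.98 |
| 5 | 0.84 | 0.91 | 0.985 |

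In every replicate each Bonferroni rejection was also a Holm rejection.

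**Step 5. Size of the loss, unequal effects.** Same settings, with 0.533 on PAPA severity and 0.3 on each other outcome:

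| m | PAPA, Bonferroni to Holm | Each other outcome, Bonferroni to Holm |
|---|---|---|
| 3 | 0.881 to 0.888 | 0.35 to 0.45 |
| 5 | 0.841 to 0.850 | 0.29 to 0.37 |

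PAPA severity gains about 1 point; the weaker outcomes gain about 9 to 10. At-least-one power is again the same for both methods.

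**Step 6. Realised error.** Under the global null the family-wise error is identical for both (m = 3: 0.049 at correlation 0, 0.045 at correlation 0.5). With one real effect among three and correlation 0, it is 0.033 for Bonferroni and 0.047 for Holm. Both are below 0.05.

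**The case against.** The case for leaving the text alone has four parts.

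- **Bonferroni does buy something.** When some effects are real, its realised family-wise error is lower (0.033 against 0.047 in step 6). It also bounds the expected number of false rejections at alpha, which Holm does not: with m = 3, correlation 0.5 and no real effects, the simulated values were 0.051 for Bonferroni, which is 0.05 within simulation noise, and 0.055 for Holm. Its simultaneous confidence intervals are simpler. A planner could coherently want the stricter rule for confirmatory outcomes. This stands, and for that reason it would be too strong to say that Bonferroni adds no error control at all. What it does not add is a better guaranteed family-wise rate, and limiting Type I error is the only purpose the SAP gives.
- **Equal effects flatter Holm.** The documents state a group difference for PAPA severity alone, and remission is binary. This stands. Step 5 shows that the gain for PAPA severity may be about one point, with the benefit going to the weaker outcomes.
- **Success on all outcomes.** With m = 5 and equal effects, power to win on every outcome goes from 0.59 to 0.81, and a reader might infer that this is the cost to the trial. The documents do not support that: nowhere do they make significance on every main outcome the criterion for success.
- **Dropout.** A reader might also apply the SAP's 1.32 variance inflation to 180 subjects and report lower power still. The SAP uses that factor to raise enrolment to 238, so the scenario departs from the plan.

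**Conclusion.** The point holds as an avoidable inefficiency. The main-outcome tests remain valid under Bonferroni, and a reader should not infer that the Type I error is uncontrolled or that the trial is less likely to show some effect: the probability of at least one significant main outcome is the same under either method.

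The direction of the loss is certain for any family of two or more outcomes. Its size is not, because the SAP does not say which outcomes are main. With the plan's effect on every outcome it is about 3 points of power per outcome for two outcomes, 5 for three and 7 for five. With a smaller effect of 0.3 on the others, and three or five outcomes, it is about 1 point for PAPA severity and 9 to 10 for each of the rest. These figures assume 90 per arm, two-sided family-wise alpha 0.05 and correlation 0.5.

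Two gaps in the same part of the plan matter more than the choice of procedure. The family of main outcomes is undefined, and the stated power of 0.97 is one-sided and unadjusted, so the cost of any correction was never counted.

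**What to change.** In General Data Analysis Considerations, replace the Bonferroni sentence with one that applies the Holm step-down procedure to a prespecified list of main outcomes, at the same family-wise alpha the plan uses. The sponsor should supply the list; the Hypothesis 1A outcomes are one example. State that alpha and its sidedness in the same sentence, since the SAP mentions sidedness only in a power calculation. In the next sentence, name Holm as the method for the other outcomes, not as an example, and define them as a separate family.

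The cost is a sentence or two, settled before outcome data are examined by group, with no new data. The downsides are small: simultaneous confidence intervals are less simple than with Bonferroni, and when some effects are null the realised family-wise error is somewhat higher, though still at most alpha.
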